- Continuous repeated measures data collected at more than one visit will be analysed using a constrained longitudinal data analysis technique (Liang 2000). The outcome (dependent variable) will consist of the baseline and postbaseline values. The model will assume a common baseline mean across the two treatment arms due to random allocation. It will incorporate time point (study visit) as a categorical variable, thus it will not assume a specific trajectory over time. In addition to study visit, the model will include treatment as the main factor and the treatment by study visit interaction. The variancecovariance among the repeated measurements will be defined as unstructured. In the case of non-convergence, we will consider alternative structures (first-order autoregressive, Toeplitz, compound symmetry). Using this model, study participants with a missing baseline or a missing postbaseline value will be included in the analysis but study participants with no outcome values will be excluded. This model will yield unbiased results when the outcome data are Missing At Random. We will report the estimate and two-sided confidence interval of the absolute difference between two treatment groups in the change from baseline to 3 months and 6 months postbaseline (if applicable). Before fitting this model, the distribution of the outcome will be explored. In addition, we will examine if there are potential violations of underlying model assumptions (e.g. residuals). As a result, we may apply an appropriate transformation (e.g. log-transformation) before fitting the final model.
- Binary data will be analysed using a logistic regression model. We will report
 the estimate and two-sided confidence interval of the odds ratio between the
 two treatment groups.
- Categorical data will be analysed using an ordinal logistic regression model.
 We will report the estimate and two-sided confidence interval of the odds ratio between the treatment groups.

Details of which model will be used for each of the primary, key secondary, and secondary outcomes can be found in Appendix 3.

Compliance

See Table 4 in **Appendix 4**.

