7.1.1 Multiple testing

The primary outcome at day 180 will be evaluated using the two-sided 5% level of significance.

Multiple testing for the key secondary outcomes related to corneal nerve parameters at day 180 will be assessed using the Benjamini-Hochberg stepwise method with a false discovery rate of 5% for: corneal nerve fibre density (CNFD), corneal nerve branch density (CNBD), central corneal sensitivity thresholds to room temperature, and central corneal sensitivity thresholds to cooled temperature. For these key secondary outcomes at day 180, we will report the multiplicity adjusted p-values.

For all other post-baseline time points and outcomes, we will report multiplicity unadjusted p-values. Given the large number of statistical tests, the probability of finding at least one false positive finding will be close to 100%. For this reason, we will exercise caution and in addition to p-values, associations will be interpreted based on the magnitude and direction of the association and width of the 95% confidence intervals.

All tests will be performed two-sided, and we will report two-sided 95% confidence intervals.

8. Sensitivity Analyses

Additional sensitivity analyses will be performed for the outcomes linked to the primary and key secondary aims for the following dataset:

- Dataset excluding participants deemed non-compliant (see definition in Section 6.3).

9. QC Plans

Source data verification of the data entered on REDCap was performed by the Principal Investigator (PI). Data was manually checked for accuracy from the source worksheets/original digital data record, for all participants, for the primary outcome (CNFL) and key secondary outcomes (CNFD, CNBD, central corneal sensitivity thresholds to room temperature, and central corneal sensitivity thresholds to cooled temperature). In addition, a subset of data comprising at least 20% of the full dataset,

was randomly selected by the PI for verification, to ensure that the observations and findings are recorded correctly and completely. Data found as incorrectly entered were verified against the original source documents, corrected on REDCap and recorded accordingly.

10. Programming Plans

A list of all planned tables and figures and their templates can be found in Appendix 4.

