Ulnar sensory amplitude, orthodromic (µV)	9.18 (4.67)	8.61 (4.18)	-0.57 (2.30)	7.15 (4.83)	7.58 (4.78)	0.53 (1.37)	-0.81 (-1.93,0.31)	0.16
• ,	(n=20)	(n=20)	(n=20)	(n=22)	(n=19)	(n=19)	(n=42)	
Ulnar sensory velocity, orthodromic (ms ⁻¹)	57.98 (5.45)	57-94 (5-21)	-0.04 (3.31)	57.40 (7.98)	56.29 (7.01)	-0.69 (4.59)	0.95 (-1.40,3.29)	0.43
	(n=20)	(n=20)	(n=20)	(n=21)	(n=18)	(n=17)	(n=41)	
Ulnar sensory latency, antidromic (ms)	31.66 (16.04)	29.87 (14.66)	-0.82 (5.51)	28.80 (17.45)	29·02 (19·19)	0.47 (9.55)	-1·19 (-6·04,3·66)	0.63
	(n=19)	(n=20)	(n=19)	(n=22)	(n=19)	(n=19)	(n=41)	
Ulnar sensory amplitude, antidromic (μV)	55.75 (6.15)	56.13 (4.83)	0.34 (5.12)	54.15 (7.51)	55.62 (8.67)	1.10 (6.09)	-0.35 (-3.73,3.02)	0.84
•	(n=19)	(n=20)	(n=19)	(n=22)	(n=18)	(n=18)	(n=41)	

Supplementary Tables and Figures

Page 9 of 16

Ulnar sensory velocity, antidromic (ms ⁻¹)	2.74 (0.28)	2.64 (0.25)	-0.09 (0.24)	2.85 (0.62)	2.71 (0.30)	-0.16 (0.50)	-0.02 (-0.16,0.11)	0.73
	(n=19)	(n=20)	(n=19)	(n=22)	(n=19)	(n=19)	(n=41)	
	Ome	ega-3 PUFAs (con	tinued)	P	lacebo (continu	Omega-3 PUFAs vs Placebo (continued)		
	Baseline $(n=20)^{\rm b}$	Day 180 (n=20) ^b	Change from baseline at day 180 (n=20)	Baseline (n=22)	Day 180 (n=19)	Change from baseline at day 180 $(n=19)$	Estimate (95% CI) Day 180 (n=42)	p- value ^a
Sural sensory latency, orthodromic (ms)	3.72 (0.27)	3.70 (0.37)	-0.02 (0.32)	3.67 (0.48)	3.72 (0.55)	-0.01 (0.42)	-0.02 (-0.25,0.21)	0.87
	(n=20)	(n=20)	(n=20)	(n=21)	(n=19)	(n=18)	(n=41)	
Sural sensory amplitude, orthodromic (μ V)	11.93 (7.11)	11.44 (6.70)	-0.49 (3.88)	12.26 (7.80)	12.27 (8.25)	-0.37 (2.84)	-0.20 (-2.26,1.86)	0.85
·	(n=20)	(n=20)	(n=20)	(n=22)	(n=19)	(n=19)	(n=42)	
Sural sensory velocity, orthodromic (ms ⁻¹)	47.79 (3.90)	48.24 (5.06)	0.45 (3.54)	48.25 (7.50)	70·91 (99·31)	24.29 (102.69)	-22.98 (-66.48,20.51)	0.30
	(n=20)	(n=20)	(n=20)	(n=21)	(n=18)	(n=17)	(n=41)	

Mean and standard deviation, unless stated otherwise. IQR=interquartile range. PUFAs=polyunsaturated fatty acids.

^ap-values are not adjusted for multiple testing.

^bOne participant in the omega-3 PUFA group completed the study but did not undergo procedures relating to small or large nerve fibre function in the limbs.

Table S7. Exploratory outcome: small nerve fibre function (quantitative sudomotor axonal reflex testing) (Intention-To-Treat sample)

	(Omega-3 PUFA	s		Placebo	Omega-3 PUFAs vs Placebo		

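### Table S6: one implied sural velocity of about 468 m/s drives the printed sural result, and the three antidromic ulnar rows carry rotated labels (all exploratory)

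*Combined protocol and SAP*

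**What the plan says.** Table S6, in the supplementary tables that follow the SAP, is headed as exploratory. Protocol section 5 lists sural velocity and the ulnar measures as exploratory items 10 and 8.

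- **Sural velocity.** Placebo is 48.25 (SD 7.50, n=21) at baseline and 70.91 (SD 99.31, n=18) at Day 180, with change 24.29 (SD 102.69, n=17). Omega-3 is 48.24 (SD 5.06, n=20) at Day 180, with change 0.45 (SD 3.54, n=20). The estimate is minus "22.98 (-66.48,20.51"), p=0.30.
- **Sural latency, placebo.** 3.67 ms (SD 0.48, n=21) at baseline and 3.72 ms (SD 0.55, n=19) at Day 180.
- **Antidromic ulnar rows, omega-3 baseline.** The row headed "Ulnar sensory latency, antidromic (ms") shows 31.66; the amplitude row (µV) shows 55.75; the velocity row (m/s) shows 2.74.

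On checks, SAP section 6 (Statistical procedures) says: "Before fitting this model, the distribution of the outcome will be explored". It also promises a look at residuals. SAP section 5 mentions regular verification of source documents during data collection. SAP section 9 verifies the primary and key secondary outcomes in full, and in addition "a subset of data comprising at least 20% of the full dataset". Neither the table footnotes nor the list of changes from the planned analysis mentions the sural value or the ulnar labels.

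**The concern.** Placebo sural velocity appears to rise by half in six months with an SD of about 100, while latency over the same segment stays flat. Every other velocity SD in the table is below 9. A reader would see a 23 m/s disadvantage for omega-3 with an interval too wide to interpret.

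In the ulnar block, a sensory latency of about 32 ms and a sensory velocity below 3 m/s cannot be reconciled with the orthodromic rows just above (2.49 ms and 57.98 m/s). Anyone extracting these rows, for a meta-analysis for example, would take a spurious effect for one nerve and the wrong quantity for another.

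**Working it through.** **1. Reproduce the printed sural result.** The SAP states: "All tests will be performed two-sided, and we will report two-sided 95% confidence intervals". So SE = (20.51 + 66.48)/(2 × 1.96) = 22.19; z = 22.98/22.19 = 1.04; p = 0.30, as printed. The pooled Day 180 SD is √[(19 × 5.06² + 17 × 99.31²)/36] = 68.34, and 68.34 × √(1/20 + 1/18) = 22.20. The inflated placebo SD therefore went into the fitted model.

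**2. What the Day 180 mean and SD imply.** Let one value x stand apart from the other n − 1, which have mean m and SD s. Then

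- d = x − m = √{[(n − 1)SD² − (n − 2)s²] × n/(n − 1)}
- m = mean − d/n

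With n=18, mean 70.91, SD 99.31 and s = 5.06 (the omega-3 SD): d = 420.8, m = 47.5, x = 468.4. Varying s from 0 to 9 moves x only from 468.8 to 467.3 and m from 47.5 to 47.6. The largest single value these figures allow is 70.91 + 17 × 99.31/√18 = 468.84, so the data sit almost at the one-outlier limit. Two equal outliers would need the other 16 to average 36.8 m/s, and three would need the rest to average 27.8; neither fits a baseline of 48.25. Assuming only non-negative velocities, at least one value is 70.91 + (17/18 × 99.31²)/70.91 = 202 m/s or more.

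**3. The change column, separately.** With n=17, mean 24.29, SD 102.69 and s = 3.54: d = 423.2, so one change is about +422.6 and the other 16 average −0.60. That puts this participant's baseline near 468 − 422 = 46 m/s, an ordinary value.

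**4. The latency row.** Mean velocity × mean latency at placebo baseline is 48.25 × 3.67 = 177 mm. At 468 m/s the latency would be 177/468 = 0.38 ms. The placebo Day 180 latency row covers all 19 participants in that column, and the smallest value it permits is 3.72 − 18 × 0.55/√19 = 1.45 ms. At 1.45 ms, 468 m/s would need about 679 mm, 3.8 times the implied mean distance.

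**5. The sural result without that value.** Raw difference in change as printed: 0.45 − 24.29 = −23.84. Without it: 0.45 − (−0.60) = +1.05. The placebo change SD without the value is not printed, so it is assumed. The low end is 3.54 (the omega-3 sural SD) and the high end 6.09 (the largest placebo velocity-change SD elsewhere in the table, taken from the relabelled ulnar row). Half-width = 1.96 × √(3.54²/20 + s²/16):

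| Assumed s | Difference | Half-width | Printed 43.5 ÷ half-width | p (normal) |
|---|---|---|---|---|
| 3.54 | +1.05 | 2.33 | 18.7 | 0.38 |
| 6.09 | +1.02 | 3.36 | 12.9 | 0.55 |

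The fitted half-widths of the other velocity rows, counting the relabelled ulnar row, run from 2.3 to 3.4.

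**6. Ulnar labels.** Omega-3 baseline:

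| Printed label | Value | Orthodromic row, same label | Fits |
|---|---|---|---|
| Latency (ms) | 31.66 | 2.49 | amplitude, µV |
| Amplitude (µV) | 55.75 | 9.18 | velocity, m/s |
| Velocity (m/s) | 2.74 | 57.98 | latency, ms |

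Velocity × latency as printed gives 2.74 × 31.66 = 87 mm (placebo 2.85 × 28.80 = 82). Relabelled, it gives 55.75 × 2.74 = 153 mm (placebo 154), close to the orthodromic ulnar figure of 57.98 × 2.49 = 144. The antidromic-to-orthodromic amplitude ratio is 55.75/9.18 = 6.1 as printed and 31.66/9.18 = 3.4 relabelled; the median nerve gives 35.72/13.53 = 2.6. The placebo Day 180 counts (19, 18, 19 down the three rows) also match the orthodromic amplitude, velocity and latency rows.

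**The case against.** The strongest reply is that nothing important turns on this. The four rows are exploratory, with p = 0.30, 0.63, 0.84 and 0.73, and SAP section 7.1.1 already asks for caution with unadjusted results. The secondary sural outcome is amplitude, at −0.20 (−2.26, 1.86), and it is untouched, as is CNFL. The model arithmetic also reproduces. All of that stands and limits the point to a table correction.

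Three stronger readings are tempting and unsupported:

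- **That the partial verification in SAP section 9 let the errors through.** The documents do not show where either error arose. SAP Appendix 1 lists the ulnar variables with the right units, so the rotation may have come in when the table was made, where source verification would not have helped. SAP sections 5 and 6 also describe other checks.
- **That the sural value is 46.8 with a lost decimal point.** This fits, but only the source record can show it.
- **That the ulnar results themselves are wrong.** Only the labels and units are.

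Could reading the PDF have rotated the labels? That is unlikely: each label sits on the line of its own values, and the rows above and below are aligned.

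**Conclusion.** The point holds as a reporting error in four exploratory rows. The sural velocity row has distorted placebo Day 180 and change summaries, estimate, interval and p-value. The estimate moves from about −23 to about +1 m/s, and the printed interval is roughly 13 to 19 times too wide. The three antidromic ulnar rows are mislabelled, with numbers that look sound.

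The individual sural value is inferred from summary statistics, though it barely depends on the assumed spread of the others. The corrected half-width does depend on the assumed placebo change SD (3.5 to 6.1), and the +1 m/s is a raw difference, not a refitted estimate. On these assumptions the corrected sural result is also expected to be non-significant. The ulnar p-values do not change with relabelling. No conclusion on CNFL or sural amplitude is affected.

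On process, the documents support only a narrow statement: the distribution and residual check promised in SAP section 6 was evidently not acted on for sural velocity.

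**What to change.** 1. Check the placebo Day 180 sural velocity near 468 m/s against the source record. Correct it, or raise a query if the record does not settle it, and refit that row.
2. Relabel the three antidromic ulnar rows after comparing them with the dataset variables named in SAP Appendix 1. If the variables themselves are swapped, correct them there too.
3. Reissue Table S6 with a note of both corrections, stating that the outcomes are exploratory.
4. Run a one-off range check on the other numeric outcomes and verify every flagged value at source.

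Amending the SAP to add a check before database lock would not help this trial: the last visit was on 10 March 2020 and the results are already tabulated. The cost is one data query, one model refit, three labels and a short script.
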